1.22 Nonclinical

A preclinical development program has been completed to support clinical trials on ponatinib. *In vitro* assays demonstrated that ponatinib potently inhibits the kinase enzymatic activity of the T315I ABL kinase domain, as well as that of the native (unmutated) enzyme. In leukemia cell lines expressing these BCR-ABL variants, ponatinib potently inhibited BCR-ABL signaling, leading to inhibition of cellular proliferation and induction of apoptosis. Ponatinib also potently inhibits the proliferation of cell lines expressing other major clinically observed imatinib-resistant mutants of BCR-ABL. *In vivo* antitumor activity has been shown in tumor-bearing mouse models.

Ponatinib is also a potent inhibitor of certain other tyrosine kinases implicated in the initiation and progression of leukemias and other tumor types. In particular, it inhibits FLT3, which is frequently mutationally activated in acute myeloid leukemia (AML), and inhibits all members of the FGFR family, which are implicated in a variety of myeloproliferative disorders and solid tumor indications. Ponatinib also inhibits several other kinases, including KIT, RET, SRC, VEGFR, PDGFR, and TIE2. Taken together, the kinase inhibition profile of ponatinib suggests the potential for clinical activity in other hematologic and nonhematologic malignancies in addition to CML.

Preclinical safety assessment studies were performed on ponatinib including 6-month oral toxicology studies in rats and cynomolgus monkeys. The rat was shown to be the most sensitive species to the toxicologic effects of ponatinib. In the 6-month oral toxicology study in rats, the no observed adverse effect level (NOAEL) was 0.25 mg/kg/day. Higher dose levels of 0.75 and 2 mg/kg/day caused mortality of some animals. Histologic examination revealed decreased

numbers of chondrocytes along the physis in the femur at the 0.75 and 2 mg/kg/day dose levels, and lymphoid depletion was observed in the thymus at the 2 mg/kg/day dose level. The administration of ponatinib to cynomolgus monkeys for 6 months at oral dose levels of 0.25, 0.75 and 2 mg/kg/day was well tolerated with no ponatinib-related microscopic findings being observed at any dose level. Toxicity studies in pregnant rats demonstrated fetal malformations and embryo-fetal toxicity at dose levels of 1 and 3 mg/kg/day, respectively, and higher. In a phototoxicity study in pigmented rats, signs of minimal ocular phototoxicity were observed at 5 and 10 mg/kg.

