2.32 Assess preliminary evaluation of FGFR2 pathway perturbation with ponatinib

2.33 To describe patient-reported health-related quality of life and symptoms

3.0 Patient Eligibility

3.1 Inclusion Criteria

3.11 Age \geq 18 years

3.12 Histological/cytological confirmation of biliary cancer.

3.13 Confirmation of advanced biliary cancer that is refractory or intolerant to gemcitabine or fluoropyrimidine based therapy with FGFR2 fusion [using Next-Gen sequencing assays (such as Foundation One®) or fluorescent in situ hybridization (FISH) break-apart assays] or FGFR pathway mutation/amplification [using Next-Gen sequencing assays (such as Foundation One®)]. Assays must be performed in a CLIA certified laboratory and done as a CLIA validated test or RUO in a CLIA laboratory.

3.14 Measurable disease as defined in Section 11.0.

3.15 ECOG Performance Status (PS) 0, 1 or 2 (Appendix I).

- 3.16 The following laboratory values obtained ≤ 14 days prior to registration.
- Absolute neutrophil count (ANC) $\geq 1500/\text{mm}^3$
 - Platelet count $\geq 100,000/\text{mm}^3$
 - Hemoglobin ≥ 9.0 g/dL
 - Total bilirubin ≤ 1.5 x upper limit of normal (ULN), unless due to Gilbert's syndrome
 - Aspartate transaminase (AST) and Alanine Aminotransferase (ALT) < 3 x ULN
 - Creatinine ≤ 1.5 x upper limit of normal (ULN)
 - Serum lipase and amylase ≤ 2.5 x upper limit of normal (ULN). Note: If subject has tumor involvement in the liver ≤ 3 x ULN.
- 3.17 Negative pregnancy test done ≤ 7 days prior to registration, for women of childbearing potential only.
- 3.18 Recovered from prior radiotherapy and/or systemic therapy related toxicities to Grade ≤ 1
- 3.19a Provide informed written consent.
- 3.19b Life expectancy ≥ 3 months
- 3.19c Willing to return to enrolling institution for follow-up (during the Active Monitoring Phase of the study).
- Note: During the **Active Monitoring** Phase of a study (i.e., active treatment and observation), participants must be willing to return to the consenting institution for follow-up.*
- 3.19d Female and male patients who are fertile agree to use an effective form of contraception with their sexual partners from registration through 4 months after the end of treatment.
- 3.19e Ability to complete questionnaire(s) by themselves or with assistance.

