3.2 Exclusion Criteria

- 3.21 Any of the following because this study involves an investigational agent whose genotoxic, mutagenic and teratogenic effects on the developing fetus and newborn are unknown:
- Pregnant women
 - Nursing women
 - Men or women of childbearing potential who are unwilling to employ adequate contraception
- 3.22 Co-morbid systemic illnesses or other severe concurrent disease which, in the judgment of the investigator, would make the patient inappropriate for entry into

this study or interfere significantly with the proper assessment of safety and toxicity of the prescribed regimens.

- 3.23 Immunocompromised patients and patients known to be HIV positive and currently receiving antiretroviral therapy. NOTE: Patients with a known history of HIV infection are not eligible for this trial.
- 3.24 Uncontrolled intercurrent illness including, but not limited to, ongoing or active infection, symptomatic congestive heart failure, unstable angina pectoris, cardiac arrhythmia, or psychiatric illness/social situations that would limit compliance with study requirements.
- 3.25 Receiving any other investigational agent which would be considered as a treatment for the primary neoplasm.
- 3.26 Prior systemic chemotherapy, radiation therapy or major surgery \leq 30 days prior to registration.
- 3.27 Concurrent use of any other approved or investigational anticancer agents, including hormonal agents
- 3.28 Prior nitrosourea or mitomycin C \leq 6 weeks prior to registration.
- 3.29a Patients with gastrointestinal comorbidities that would affect intake or absorption of ponatinib
- 3.29b Untreated or progressive brain metastases
- 3.29c Prior treatment with or allergic reactions attributed to compounds of similar chemical or biologic composition to ponatinib
- 3.29d Clinically uncontrolled hypertension (diastolic blood pressure >90 mm Hg; systolic >140 mm Hg). NOTE: Patients with hypertension should be undergoing treatment at study entry for blood pressure control.
- 3.29e Previous or concurrent malignancy except adequately treated basal or squamous cell skin cancer, in situ carcinoma of the cervix, or other solid tumor treated curatively and without evidence of recurrence for at least 5 years
- 3.29f History of significant bleeding disorder unrelated to cancer
- 3.29g History of acute pancreatitis within 1 year prior to registration, chronic pancreatitis, alcohol abuse or uncontrolled hypertriglyceridemia (triglycerides >450 mg/dL)

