4.0 Test Schedule

Cycle = 28 days

Tests and procedures	Active Monitoring Phase						
	≤14 days prior to registration	Cycle 1 Day 1 (± 2 days) prior to treatment	Cycle 1 Days 8, 15, 22 prior to treatment	Cycle 2 and beyond Day 1 (± 2 days) prior to treatment	Q 8 weeks from Cycle 1 Day 1 (± 5 days)	Every 3 Cycles starting at end of Cycle 3 (± 5 days)	End of treatment
History and exam, wt, ECOG	X			X			X
Height, Child Pugh score	X						
Vitals ³	X	X	X	X			X
Hematology group WBC, ANC, Hgb, PLT	X	X	X	X			X
Chemistry group Sodium, potassium, chloride, bicarbonate, total protein, albumin, calcium, glucose, BUN, total bilirubin, creatinine, alkaline phosphatase, SGOT (AST), SGPT (ALT)	X	X		X			X
Amylase ^R	X	X	X	X			
Lipase ^R	X	X	X	X			
CA19-9		X		X ⁵			
EKG ^R	X					X	
Echocardiogram	X			X ¹⁰			
Tumor measurement and Imaging (CT or MRI as clinically)	X ¹				X ²		

indicated)							
Pregnancy test	X ⁴						
Patient questionnaire booklet	X ⁹			X ⁹			
Adverse event assessment	X		X	X			
Research Archival Tissue (optional)	X ⁸						
Research Tissue Biopsy (optional)				X ^{7,R}			X ⁶
Research blood samples (Optional)	X			X			X

1. Imaging studies such as CT scans, and MRIs can be performed ≤ 28 days prior to registration. Use same imaging throughout the study. Assessment by physical exam should be done ≤ 14 days prior to registration.
 2. Tumor assessment must be performed at least every 8 weeks. Tumor assessment should be performed at any time during the treatment cycle that disease progression is clinically suspected so that patient can go off treatment and receive other therapy.
 3. Includes weight, blood pressure, pulse and temperature
 4. Women of childbearing potential only. Must be done ≤ 7 days prior to registration.
 5. Only to be collected if $> \text{ULN}$ on Cycle 1 Day 1
 6. If patient has experienced disease progression and at such time a standard of care biopsy is ordered by the treating physician, waste specimen will be collected, fresh frozen and stored for future correlative studies. Perform only if archival specimen was available.
 7. Perform only if archival specimen was available.
 8. Archival FFPE and/or fresh frozen tissue collected in setting of standard of care procedures.
 9. Patient questionnaire booklet must be used; copies are not acceptable for this submission. Booklet should be completed by patient prior to review of treatment response and discussions of patient's general health since last treatment evaluation.

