6.4 An optional correlative research component is part of this study, there will be an option to select if the patient is to be registered onto this component (see Sections 14.0 and 17.0).

- Patient has/has not given permission to have a tissue biopsy at cycle 2, day 1.
 - Patient has/has not given permission to allow any excess tissue collected while on this study to be used for research studies
 - Patient has/has not given permission for blood collection at screening, Prior to each cycle, and at end of study to be used for research studies.
- 6.5 At the time of registration, the following will be recorded:
- Patient has/has not given permission for his/her tissue and blood sample(s) to be stored and used in future research of biliary cancer at Mayo Clinic
 - Patient has/has not given permission for his/her tissue and blood sample(s) to be stored and used in future research at Mayo Clinic to learn about, prevent, or treat any other health problems
 - Patient has/has not given permission for Mayo Clinic to give his/her tissue and blood sample(s) to researchers at other institutions
- 6.6 Treatment cannot begin prior to registration and must begin ≤ 7 days after registration.
- 6.7 Pretreatment tests/procedures (see Section 4.0) must be completed within the guidelines specified on the test schedule.
- 6.8 All required baseline symptoms (see Section 10.6) must be documented and graded.
- 6.9a Treatment on this protocol must commence at a Mayo Clinic institution under the supervision of a medical oncologist.
- 6.9b Study drug is available on site.
- 6.9c Patient questionnaire booklet is available on site; copies are not acceptable for this submission.

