10.55 Pregnancy

To ensure patient safety, each pregnancy occurring while the patient is on study treatment must be reported to ARIAD within 24 hours of learning of its occurrence. The pregnancy should be followed up to determine outcome, including spontaneous or voluntary termination, details of the birth, and the presence or absence of any birth defects, congenital abnormalities, or maternal and/or newborn complications.

Pregnancy should be recorded on a Clinical Study Pregnancy Form and reported by the investigator to the oncology ARIAD Drug Safety and Epidemiology (DS&E) department. Pregnancy follow-up should be recorded on the same form and should include an assessment of the possible relationship to the ARIAD study treatment of any pregnancy outcome. Any SAE experienced during pregnancy must be reported on the SAE Report Form.

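### The only pregnancy test is timed from registration, so it can be 14 days old at the first ponatinib dose, and the test schedule includes no repeat

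*Combined protocol and SAP*

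**What the plan says.** **Timing of the test.** Inclusion criterion 3.17 asks for a "Negative pregnancy test done ≤ 7 days prior to registration, for women of childbearing potential only". Footnote 4 to the Section 4.0 schedule agrees: "Women of childbearing potential only. Must be done ≤ 7 days prior to registration". The pregnancy row in that table is marked in the pre-registration column and nowhere else.

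**Start of treatment.** Section 6.6 states: "Treatment cannot begin prior to registration and must begin ≤ 7 days after registration".

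**Why pregnancy is excluded.** Section 3.21 excludes pregnant and nursing women, and anyone of childbearing potential unwilling to use contraception. The reason given is that the agent's "genotoxic, mutagenic and teratogenic effects on the developing fetus and newborn are unknown". Section 1.22 reports: "Toxicity studies in pregnant rats demonstrated fetal malformations and embryo-fetal toxicity". The Medication Guide in Appendix XI tells patients that the drug can harm an unborn child.

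**Other safeguards.** Under 3.19d, fertile patients of either sex agree to "use an effective form of contraception with their sexual partners from registration through 4 months after the end of treatment". Appendix XI tells women not to become pregnant and to report a pregnancy promptly. Section 4.0 schedules history and exam on Day 1 of each cycle from Cycle 2, and 7.2 requires a return visit at least every 28 days. Section 10.55 covers reporting and follow-up of any pregnancy that becomes known.

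**The concern.** The exclusion in 3.21 exists to prevent fetal exposure to ponatinib, and exposure begins at the first dose. The check that supports it is tied to registration, an administrative date that can fall a week before dosing. A woman who tested negative early in the window, and conceived or was in very early pregnancy at that time, could receive her first dose with every rule in the plan followed.

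Dosing is then daily, and under 13.1 it continues while the patient has a response or stable disease. The schedule contains no later test. What is at stake is participant safety for a small group, where the possible harm is serious and cannot be reversed. Investigators are also given inconsistent descriptions of that harm, because the stated ground for the exclusion differs from the nonclinical section and the patient guide.

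**Working it through.** The plan states no figure on this point, so there is none to reproduce. The check is addition of the plan's own windows, followed by a side-by-side reading.

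**Step 1. Age of the test at first dose.**
- Test to registration: 0 to 7 days (3.17; 4.0 footnote 4).
- Registration to first dose: 0 to 7 days (6.6).
- Minimum age: 0 + 0 = 0 days. Maximum age: 7 + 7 = 14 days.

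The Cycle 1 Day 1 column carries a ±2-day window. Section 6.6 is a firm limit, so I have not added those 2 days.

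**Step 2. Age of the last scheduled test on treatment.**
- A cycle is 28 days. The stable-disease route to success (16.11) needs 4 or more cycles: 4 × 28 = 112 days.
- With no repeat, the last test could be up to 14 + 112 = 126 days old by the end of Cycle 4, and older if treatment continues.

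**Step 3. Cover between test and first dose.**

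| Interval | Maximum length | 3.19d contraception commitment | Later scheduled test |
|---|---|---|---|
| Test to registration | 7 days | No, starts at registration | No |
| Registration to first dose | 7 days | Yes | No |
| On treatment | Open-ended | Yes | No |

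**Step 4. What is re-checked at first exposure.** Section 4.0 repeats vitals, hematology, chemistry, amylase and lipase on Cycle 1 Day 1 before treatment. Pregnancy status is not among them.

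**Step 5. The descriptions of fetal risk.** Section 3.21 treats genotoxic, mutagenic and teratogenic effects together as unknown. Section 1.22 reports fetal malformations in rats. Appendix XI states, without qualification, that an unborn child can be harmed. The conflict is confined to the teratogenic part of the 3.21 wording.

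**Step 6. Number of women concerned.** Section 16.63 expects 15 women among 30 patients (50%). The documents do not give the share of childbearing potential, so the range is 0 to 15. If the trial stopped after 10 patients at Stage 1, the same 50% would give 10 × 0.5 = 5 women, and the range would be 0 to 5.

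**The case against.** The strongest reply is that the plan manages reproductive risk mainly by contraception, with the test as an entry check. Sections 3.19d and 3.21 make contraception a condition of entry, Appendix XI adds a warning and an instruction to report, and history is taken each cycle. Timing eligibility tests from registration is also this protocol's general convention: 3.16 allows 14 days for laboratory values, and the pregnancy test has a tighter limit of 7. This stands as mitigation. It does not remove the gap, because none of these measures verifies status at first exposure and the contraception commitment does not reach back before registration.

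Several stronger readings are tempting, and the documents do not support them:

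- *That 3.17 and 6.6 contradict each other.* They do not. Footnote 4 matches 3.17, and 6.6 sets a separate window. The 14 days arise from following both.
- *That a pregnancy on treatment would surface only through symptoms.* Scheduled history-taking and self-report are routes to detection, though weaker than a test.
- *That 10.55 conflicts with the schedule.* It says "each pregnancy occurring while the patient is on study treatment must be reported to ARIAD within 24 hours", but the sentence goes on to count the 24 hours from learning of the pregnancy. The duty arises by whatever route the pregnancy is learned of and does not presuppose scheduled testing.
- *That a specific number of women is affected.* Any such figure needs an assumed childbearing share that the documents do not give. Being subject to the schedule is also not the same as being harmed.

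Two further replies have some force. Rat findings do not settle human effects, so 1.22 alone would leave the 3.21 wording defensible; the unqualified warning in Appendix XI is harder to square with it. The consent pages and the patient information sheet (Appendix III) are not in the reviewed text, so any further pregnancy instructions there cannot be checked.

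**Conclusion.** The concern holds in a limited form. Under the plan as written, a first dose may be given on a pregnancy test up to 14 days old. Up to 7 of those days are covered neither by the 3.19d commitment nor by a later test, and no repeat is scheduled on treatment. The 14 days is a worst case that assumes both windows are fully used; the age can also be 0.

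The wording of 3.21 is a separate, smaller inconsistency. Pregnant women are excluded either way, but the three descriptions of fetal risk should agree.

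This is a participant-safety gap in the schedule that is worth closing because it is cheap to close. It does not show that reproductive risk is unmanaged, since contraception, warning and reporting are all in place. It has no bearing on the Simon two-stage design, its error rates or the primary analysis.

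**What to change.** 1. Reconcile 3.17, Section 4.0 footnote 4 and 6.6 with the exclusion in 3.21, so that pregnancy status is verified relative to the first dose and not only to registration.
2. Have the sponsor decide, and state in Section 4.0, whether the test is repeated on treatment and, if so, when. No interval is proposed here.
3. Align the description of fetal risk in 3.21 with 1.22 and Appendix XI.

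The cost is mainly wording in one criterion, one footnote, one table row and the 3.21 rationale. If the sponsor adds tests, there would be a few extra assays that could be done at visits already scheduled. Pregnancy tests are not on the research-funded list in 19.2, so any repeat would need a decision on who pays. The protocol does not say whether the test is on blood or urine, so it should not be assumed that existing blood draws would cover it.

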3.2 Exclusion Criteria

- 3.21 Any of the following because this study involves an investigational agent whose genotoxic, mutagenic and teratogenic effects on the developing fetus and newborn are unknown:
- Pregnant women
 - Nursing women
 - Men or women of childbearing potential who are unwilling to employ adequate contraception
- 3.22 Co-morbid systemic illnesses or other severe concurrent disease which, in the judgment of the investigator, would make the patient inappropriate for entry into

this study or interfere significantly with the proper assessment of safety and toxicity of the prescribed regimens.

- 3.23 Immunocompromised patients and patients known to be HIV positive and currently receiving antiretroviral therapy. NOTE: Patients with a known history of HIV infection are not eligible for this trial.
- 3.24 Uncontrolled intercurrent illness including, but not limited to, ongoing or active infection, symptomatic congestive heart failure, unstable angina pectoris, cardiac arrhythmia, or psychiatric illness/social situations that would limit compliance with study requirements.
- 3.25 Receiving any other investigational agent which would be considered as a treatment for the primary neoplasm.
- 3.26 Prior systemic chemotherapy, radiation therapy or major surgery \leq 30 days prior to registration.
- 3.27 Concurrent use of any other approved or investigational anticancer agents, including hormonal agents
- 3.28 Prior nitrosourea or mitomycin C \leq 6 weeks prior to registration.
- 3.29a Patients with gastrointestinal comorbidities that would affect intake or absorption of ponatinib
- 3.29b Untreated or progressive brain metastases
- 3.29c Prior treatment with or allergic reactions attributed to compounds of similar chemical or biologic composition to ponatinib
- 3.29d Clinically uncontrolled hypertension (diastolic blood pressure >90 mm Hg; systolic >140 mm Hg). NOTE: Patients with hypertension should be undergoing treatment at study entry for blood pressure control.
- 3.29e Previous or concurrent malignancy except adequately treated basal or squamous cell skin cancer, in situ carcinoma of the cervix, or other solid tumor treated curatively and without evidence of recurrence for at least 5 years
- 3.29f History of significant bleeding disorder unrelated to cancer
- 3.29g History of acute pancreatitis within 1 year prior to registration, chronic pancreatitis, alcohol abuse or uncontrolled hypertriglyceridemia (triglycerides >450 mg/dL)
- 3.29h Clinically significant, uncontrolled, or active cardiovascular disease, specifically including, but not restricted to:
 - Any history of myocardial infarction, stroke, or revascularization
 - Unstable angina or transient ischemic attack within 6 months prior to registration

- Congestive heart failure within 6 months prior to registration, or left ventricular ejection fraction (LVEF) less than lower limit of normal per local institutional standards within 6 months prior to registration
 - History of clinically significant (as determined by the treating physician) atrial arrhythmia
 - Any history of ventricular arrhythmia
 - Active venous thromboembolism including deep venous thrombosis or pulmonary embolism that is not amenable to treatment with anticoagulants.
 - Patients with congenital prolonged QT syndromes and abnormal baseline prolonged QTc (>450 ms in men and >470 ms in women).
 - Patients with an ejection fraction $\leq 50\%$ as assessed by a baseline echocardiogram.
- 3.29i Taking medications that are known to be associated with Torsades de Pointes (see Appendix XII)
- 3.29j Taking any medications or herbal supplements that are known to be strong inhibitors of CYP3A4 ≤ 14 days prior to registration. (see Section 9.9b)

